1.11. LABORATORY REQUIREMENTS

A central laboratory will analyze the clinical laboratory safety samples (hematology, serum chemistry) the serum pregnancy test and Urinalysis, as described in [Section 1.5.4](#) for this study. Laboratory samples for safety and biomarker analyses (NTFs, anti-inflammatory markers and cytokines) will be sent to an independent laboratory for processing and analysis as specified by the Sponsor.

1.12. INVESTIGATOR AND ADMINISTRATIVE REQUIREMENTS

1.12.1. Ethics

The Sponsor/Investigator will obtain, from the clinical sites IRB, prospective approval of the clinical protocol and corresponding informed consent form(s); modifications to the clinical protocol and corresponding informed consent forms, and advertisements (i.e., directed at potential research participants) for study recruitment.

The only circumstance in which a deviation from the current IRB-approved clinical protocol/consent form(s) may be initiated in the absence of prospective IRB approval is to eliminate an apparent immediate hazard to the research subject(s). In such circumstances, the Sponsor/Investigator will promptly notify the clinical sites IRB of the deviation.

Changes to the protocol to minimize or eliminate immediate hazards or to protect the life and well-being of research participants (e.g., to limit exposure to COVID-19) may be implemented without IRB approval or before filing an amendment to the IND (FDA guidance on Conduct of Clinical Trials of Medical Products during COVID-19 Pandemic).

The clinical sites IRB operate in compliance with FDA regulations at 21 CFR Parts 50 and 21 CFR 56, and in conformance with applicable International Conference on Harmonization (ICH) E6 Guidelines on GCP.

In the event that the clinical sites IRB require, as a condition of approval, substantial changes to a clinical protocol submitted under an FDA-accepted IND application, or in the event of the Sponsor-Investigator's decision to modify the previously accepted clinical protocol the Sponsor/Investigator will submit (i.e., in advance of implementing the change) a Protocol Amendment to the IND describing any change to the protocol that significantly affects the safety of participants, the scope of the investigation, or the scientific quality of the study.

Examples of clinical protocol changes requiring the submission of a Protocol Amendment include:

- Any significant change in the number of participants under study.
- Any significant change in the design of the protocol (such as the addition or deletion of a control group).
- The addition of a new test or procedure that is intended to improve monitoring for, or reduce the risk of, a side effect or AE; or the dropping of a test intended to monitor the safety of the investigational drug.

1.12.2. Data Quality Assurance

1.12.2.1. Data Management

Data from the study will be entered into a validated electronic 21CFR Part 11 compliant database. Data review, coding, and logic, range, cross-form, and consistency checks will be performed to ensure quality of the data. Adverse events and medications will be coded using MedDRA and the World Health Organization Drug Dictionary (WHO-DD), respectively.

1.12.2.2. Electronic Case Report Forms (eCRFs)

The study will use an electronic data capture system. All personnel accessing the electronic data capture system will be trained on the use of the system by the CRO responsible for data management. The CRO responsible for clinical data management will develop e-CRFs to collect all protocol-required data for this trial that will be recorded at the investigational sites. All eCRFs are to be filled out completely, reviewed, and signed by the Investigator or sub-investigators listed on the Form FDA 1572.

Missing protocol-specified information (e.g., from missed study visits or study discontinuations) due to the COVID-19 pandemic as well as changes in study visit schedules, missed visits, or patient discontinuations that may lead to missing information for protocol-specified procedures, should be captured in the electronic case report form as applicable, noting the reason for the missing data, including the relationship to the COVID-19 pandemic.

1.12.2.3. Study Monitoring

The Sponsor or designee will monitor this study in accordance with ICH E6 GCP guidelines as detailed in the monitoring plan. By signing this protocol, the Investigator grants permission to the Sponsor or designee and appropriate regulatory authorities to conduct onsite monitoring of all appropriate study documentation. To ensure the accuracy of data collected on the eCRFs, it is mandatory that Sponsor representatives (e.g. study monitor) have direct access to original source documents (e.g. paper or electronic subject records, subject charts, and laboratory reports) needed to verify the entries on electronic case report forms. During the review of these documents, the anonymity of the subject will be respected with strict adherence to professional standards of confidentiality.

A study monitor will contact and visit the site regularly and will be allowed, on request at a mutually acceptable time, to inspect the various original medical records (paper or electronic) related to the study. The study monitor will be responsible for inspecting the eCRFs at regular intervals throughout the study, to verify the adherence to the protocol, and the completeness and correctness of all eCRF entries. The Investigator agrees to cooperate with the study monitor to ensure that any problems detected in the course of these monitoring visits are resolved.

Study monitoring will be conducted in consideration of the outbreak of the COVID-19 pandemic and in accordance with individual institutional guidelines.

1.12.2.4. Study Audits

During the course of the study and after study completion, it is possible that one or more quality assurance audits will be undertaken by authorized Sponsor representatives. The purpose of the audit is to ensure that the study is (or was) conducted and monitored in compliance with the protocol as well as recognized ICH E6 GCP guidelines and country specific regulations. If such audits occur, they will be arranged for a reasonable and agreed upon time. By signing this protocol, the Investigator grants permission to the Sponsor or designee to conduct onsite audits of all appropriate facilities and study documentation.

1.12.3. Investigational Product Accountability

NurOwn® are autologous MSC-NTF cells prepared on a per-subject basis.

At the end of the production process, the subject's MSC-NTF cells are loaded in the syringe and shipped to the medical center for transplantation.

Any syringe not administered to the subject will be immediately discarded as biohazard waste.

The manufacturing facility will be responsible for maintaining production records. The site will confirm that the syringe was administered to each subject at each treatment session.

1.12.4. Compensation, Insurance, and Indemnity

The subject will be appropriately treated or compensated, or both, for any health or other problems arising from participation in this study. In the event of a side effect or injury, appropriate medical care as determined by the Investigator or designated alternate will be provided.

If bodily injury is sustained, resulting directly from the use of the study drug or by required study procedures, the Sponsor will reimburse for reasonable physician fees and medical expenses necessary for treatment of only the bodily injury that is not covered by the subject's medical or hospital insurance, provided that the injury is not due to a negligent or wrongful act or omission by the study doctor and study staff.

1.12.5. Data recording/ eCRF Completion

The eCRFs will be completed for each subject enrolled into the clinical study. The Investigator will review, approve and sign each completed eCRF; the Investigator's signature serving as attestation of the Investigator's responsibility for ensuring that all clinical and laboratory data entered on the eCRF are complete, accurate and authentic.

Source Data are the clinical findings and observations, laboratory and test data, and other information contained in Source Documents. Source Documents are the original records (and certified copies of original records), including, but not limited to, hospital medical records, physician or office charts, physician or nursing notes, subject diaries or evaluation checklists, pharmacy dispensing records, recorded data from automated instruments, x-rays, etc. Information recorded on the eCRF shall match the Source Data recorded on the Source Documents.

Any clinical study data that will be recorded directly on the eCRF, whereupon the eCRF data is to be considered the Source Data, will be identified.

Subject names will not be supplied to the Sponsor. Participants will be identified by a unique subject number that will be recorded in the eCRF. Subject names appearing on any other document (e.g., laboratory report) must be redacted on the copy of the document to be supplied to the Sponsor. Study findings stored on a computer will be stored in accordance with data protection laws. The participants will be informed that representatives of the Sponsor, IRB, or regulatory authorities may inspect their medical records to verify the information collected, and that all personal information made available for inspection will be handled in strictest confidence and in accordance with local data protection laws.

1.12.6. Record maintenance and retention

The Sponsor and Investigator will maintain records in accordance with country specific regulations and ICH E6 GCP guidelines.

The Investigator will retain the specified records and reports for up to 2 years or longer as per requirements of local or country specific regulations after the marketing application is approved for the investigational drug; or, if a marketing application is not submitted or approved for the

investigational drug, until 2 years after investigations under the IND have been discontinued and the FDA so notified.

1.12.7. Study Termination

The Sponsor will terminate this study following completion of the study objectives, or earlier if deemed necessary.

The Sponsor reserves the right to terminate the study at any time and for any reason. When the Sponsor is aware of information on matters concerning the quality, efficacy, and safety of the study drug, as well as other important information that may affect proper conduct of the clinical study, the Sponsor may terminate the study and send a written notice of the termination along with the reasons to the Investigator.

If an Investigator intends to terminate participation in the study, the Investigator must immediately inform the Sponsor and provide the reason for it.

1.13. USE OF STUDY INFORMATION AND PUBLICATION

All clinical and laboratory information and data obtained during the conduct of the study will be considered strictly confidential. Genetic samples and data will be handled with the same high standards of confidentiality as all clinical data and according to local and federal regulations. Written permission from the Sponsor is required before disclosing any data or information relative to this study. All publications (e.g., manuscripts, abstracts, and slide presentations) based on this study must be submitted to the Sponsor for corporate review at least 60 days before submission.

1.15. APPENDICES

1.15.1. Appendix 1: Listing of study activities

1.15.1.1. Scheduled monitoring events

Table 1 Schedule of Assessments:

Study Period	Pre-treatment period					Cells/Placebo Transplantation period						Post-transplantation follow-up		
	Screening period													
Visit	V1	V2	V3	V4 ¹	V5	V6	V7	V8	V9	V10	V11	V12	V13	V14 ¹²
Procedure	Screening	ALSFRS-R Assessments		Randomization	BMA	Cell Transplantation (T1)			Cell Transplantation (T2)		Cell Transplantation (T3)			
Time Schedule	Week -18-20 (± 7 days)	Week -14 to-16 (± 7 days)	Week -10 to -12 (± 7 days)	Week -6 to-9	Week -5 to -6 ¹⁰	Day 0 - Day 3 ¹¹	Week 2 (± 3 days)	Week 4 (± 3 days)	Week 8 ¹¹ (± 5 days)	Week 12 (± 5 days)	Week 16 ¹¹ (± 5 days)	Week 20 (± 5 days)	Week 24 (± 5 days)	Week 28 (± 5 days)
Informed consent	√													
Eligibility criteria	√			√										
Demographic data	√													
Height	√													
Body weight	√		√			√		√	√	√	√	√	√	√
Physical examination	√					√		√	√	√	√	√	√	√
12 lead ECG	√					√			√		√			
Vital signs ²	√	√	√	√	√	√	√	√	√	√	√	√	√	√
Medical History	√													
ALS Medical History ³	√													

Study Period	Pre-treatment period					Cells/Placebo Transplantation period						Post-transplantation follow-up		
	Screening period													
Visit	V1	V2	V3	V4 ¹	V5	V6	V7	V8	V9	V10	V11	V12	V13	V14 ¹²
El Escorial Criteria	√													
ALSFRS-R ⁴	√	√	√	√		√	√	√	√	√	√	√	√	√
Neurological Examination	√			√		√	√	√	√	√	√	√	√	√
Slow Vital Capacity (SVC)*	√					√			√		√			√
Prior/Concomitant medication review	√	√	√	√	√	√	√	√	√	√	√	√	√	√
HIV 1 and 2	√			√										
HBV	√			√										
HCV	√			√										
Pregnancy test (for women with childbearing potential)	√			√				√		√				√
Hematology ⁵	√			√		√			√		√		√	√
Blood biochemistry ⁶	√			√		√			√		√		√	√
Coagulation tests ⁷	√			√		√			√		√			
Blood collection for biomarkers ⁸						√	√	√	√	√	√	√		
Urinalysis ⁹	√			√		√			√		√		√	√
Bone marrow aspiration					√									
Transplant (IT)						√			√		√			
CSF collection						√	√	√	√	√	√	√		
Visual inspection of injection site						√			√		√			

Study Period	Pre-treatment period					Cells/Placebo Transplantation period						Post-transplantation follow-up		
	Screening period													
Visit	V1	V2	V3	V4 ¹	V5	V6	V7	V8	V9	V10	V11	V12	V13	V14 ¹²
Adverse events review		√	√	√	√	√	√	√	√	√	√	√	√	√
C-SSRS	√										√			√
Assessment of blinding (Subject, Investigator and person doing ALSFRS-R assessments)						√								√

Abbreviations: ALS=Amyotrophic Lateral Sclerosis; ALFRS-R=ALS Functional Rating Scale–Revised; CMV=cytomegalovirus; CSF=cerebral spinal fluid; C-SSRS=Columbia-Suicide Severity Rating Scale; ECG=electrocardiogram; HIV=human immune deficiency virus; HBV=hepatitis B virus; HCV=hepatitis C virus; IT=intrathecal; V=visit

* SVC will be performed when permitted, following resolution of COVID-19 per institutional guidance

- 1 Driven by manufacturing availability. Prior to randomization complete a request for randomization form for Medical Monitor review and approval
- 2 ,Blood pressure, Body temperature, Pulse and respiratory rate (after sitting for at least 3 minutes)
- 3 ALS Medical History to collect type and duration of ALS symptoms and Date of Diagnosis
- 4 Every effort will be made to collect the ALSFRS-R scores in-person, however by exception it may be collected by telephone.
- 5 Hematology: Complete blood count (red blood cells with indices, white blood cells with differential and platelet count, hemoglobin, hematocrit)
- 6 Blood Biochemistry: Sodium, Potassium, Calcium, Bicarbonate, blood urea nitrogen, Creatinine, Glucose, Chloride, Magnesium, Phosphorus, total protein, triglycerides, Total cholesterol, high-density lipoprotein, low-density lipoprotein, urea, total bilirubin, aspartate aminotransferase (glutamic oxaloacetic transaminase), alanine aminotransferase (glutamic pyruvic transaminase), alkaline phosphatase, uric acid
- 7 Coagulation: Prothrombin time (PT), Partial thromboplastin (PTT).
- 8 Blood samples for analysis of T regulatory cells will be collected at V6, V7 and V8 only
- 9 Urinalysis - Specific Gravity, pH, glucose, protein, ketones, blood
- 10 Bone marrow derived mononuclear cells or MSC derived from the Bone Marrow aspirated at Visit 5, will be collected for DNA isolation and genetic analyses
- 11 A more flexible window may be applied to the key study visits, Randomization (V4), BMA (V5), T1 (V6), T2 (V9) and T3 (V11) that are scheduled based on manufacturing availability.

Brainstorm Cell Therapeutics		
Phase 3 Clinical Protocol BCT-002 US Amendment 2.1: March 2020	NurOwn® (MSC-NTF cells)	Page 60 of 66

- 12 An ET visit will be conducted only for participants who discontinue the study after treatment, post Visit 6. The ET visit will include all the procedures required at study Visit 14. For participants who refuse further clinic study visits, telephone contact by study staff shall be attempted and documented to review for adverse events at each scheduled visit through the remainder of study.

Table 2 Detailed Schedule of Assessments for Cell Transplantation Visits (V6, V9 and V11)

Estimated Time	06:00-14:00	12:00-14:00	14:00-16:00	16:00-18:00	19:00-21:00	08:00-10:00	12:00-14:00	
Time\ Procedure	Up to 6 hours before transplant	Hr. 0	Hr. 2 (±15 min)	Hr. 4 (±15 min)	Hr. 7 (±30 min)	Hr. 20 (±30 min)	Approximately Hr. 24 (±30 min)	Hr. ≥ 24-72 (before discharge ±30 min)
Admit to Inpatient Ward	√							
Body weight	√							
Physical Examination	√						√	
Vital signs ¹	√		√	√	√	√	√	√
12 lead ECG ²	√ ²						√ ²	
ALSFRS-R	√							
Slow Vital Capacity (SVC)*	√							
Neurological Examination	√							
Concomitant medication review ³	√		√	√	√	√	√	√
Hematology ⁴	√					√		
Blood biochemistry ⁵	√					√		
Urinalysis ⁶	√					√		
Coagulation ⁷	√					√		
Blood collection for biomarkers ⁸	√					√		
Cell Transplant IT ⁹		√						
Retention of CSF sample		√						
Visual inspection of injection site			√			√ ⁹		
Adverse events review ³	√		√	√	√	√	√	√
C-SSRS ¹⁰	√							
Assessment of blinding (Participant and Investigator) ¹¹								√
Discharge from Inpatient Setting								√

Brainstorm Cell Therapeutics		
Phase 3 Clinical Protocol BCT-002 US Amendment 2.1: March 2020	NurOwn® (MSC-NTF cells)	Page 62 of 66

Abbreviations: ALS=Amyotrophic Lateral Sclerosis; ALFRS-R=ALS Functional Rating Scale–Revised; CSF=cerebral spinal fluid; C-SSRS=Columbia-Suicide Severity Rating Scale ECG=electrocardiogram; IT=intrathecal

* SVC will be performed when permitted, following resolution of COVID-19 per institutional guidance

- 1 Pulse rate, Blood pressure, Respiratory rate, Body temperature at the designated time-points. At 2, and 4 hours \pm 15 minutes. At 8, 20 and 24 hours \pm 30 minutes
- 2 ECG will be performed at Visits 6, 9 and 11 – Time Window: +/- 30 min.
- 3 Concomitant medications and AEs will be monitored and ongoing data will be collected throughout the study visit, as necessary
- 4 Hematology: Complete blood count (Red blood cells with Indices, white blood cells with differential and platelet count, hemoglobin, hematocrit) - Time Window: +/- 30 min.
- 5 Blood Biochemistry: Sodium, Potassium, Calcium, Bicarbonate, blood urea nitrogen, Creatinine, Glucose, Chloride, Magnesium, Phosphorus, total protein, triglycerides, Total cholesterol, high-density lipoprotein, low-density lipoprotein, urea, total bilirubin, aspartate aminotransferase (glutamic oxaloacetic transaminase), alanine aminotransferase (glutamic pyruvic transaminase), alkaline phosphatase, uric acid - Time Window: +/- 30 min.
- 6 Urinalysis - Specific Gravity, pH, glucose, protein, ketones, blood. Time Window: +/- 2 hours
- 7 Coagulation: Prothrombin time (PT), Partial thromboplastin time (PTT). Time Window: +/- 30 min.
- 8 Blood samples for analysis of T regulatory cells will be collected at V6 only
- 9 Time Window: +/- 1 hour
- 10 C-SSRS assessment will be performed at Visit 11 only.
- 11 At Visit 6 assessment of blinding is performed prior to discharge

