1.5.7. Safety Follow-Up

For participants who refuse further clinic study visits, telephone contact by study staff shall be attempted and documented to review for AEs at each scheduled visit through the remainder of the study. AEs and serious adverse events will be followed up as described in [Section 1.8](#).

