1.8.5.2. Subject Withdrawal from Study

Participants may voluntarily withdraw from the study at any time during the course of the study for any reason, specified or unspecified, and without prejudice. The Investigator will document the reason/circumstances for withdrawal in the appropriate eCRF.

Participants can discontinue from the study for any of the following reasons:

- Participants whose MSC or MSC-NTF cells fail to proliferate and to produce a sufficient number of cells for transplantation (See Section 1.3.1)
- For any reason related to safety or tolerability
- At the subject's request
- At the discretion of the Investigator, if deemed appropriate for any reason
- At the discretion of the Sponsor, if deemed appropriate for any reason

Efforts will be made to follow all participants who discontinue study for any reason and encourage participant to return to the site for an End of Study visit (Visit 14). Such follow-up will include all relevant evaluations for safety and efficacy including clinical assessments and collection of laboratory study results as set out in this protocol.

Efforts will be made to have participants who discontinue from the study for any reason, return to the site for an End of Study follow up visit. Such follow-up will include all relevant evaluations for safety and efficacy including clinical assessments and collection of laboratory study results as set out in this protocol.

If a participant refuses to return for any further clinic visits, every effort will be made to follow the patient over the phone for the remaining study visits. This should be documented in the End of Study page eCRF in the electronic database including the reason/circumstances for withdrawal in a timely manner (preferably within 24-48 hours). The documentation should include the date the participant withdrew consent/discontinued, the reason for discontinuation, and the fact that the participant refuses to return for the end of study visit. The date documented will be considered the last date of contact and thus the participant's last day on study. Despite discontinuing from the study, if the site becomes aware of any adverse events or SAEs within 12 weeks of the last transplant, they should be recorded in the database adverse event log.

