1.9.1. Primary Endpoint

1.9.1.1. Efficacy

The primary efficacy endpoint will be to evaluate the proportion of NurOwn® treated participants with a ≥ 1.25 points/month improvement in post-treatment slope vs. pre-treatment slope in ALSFRS-R score at 28 weeks following the first treatment as compared to placebo.

Efficacy assessments will be based upon the 12 item ALSFRS-R total score and its subscale scores as described in [Appendix 2](#). ALSFRS-R scores should be collected in-person. Participants who refuse clinic study visits (or temporarily unable to attend) will be contacted by phone call by the trained site personnel.

The ALSFRS-R is a quickly administered (10 minutes) ordinal, validated rating scale (ratings 0-4) used to determine participants' assessment of their capability and independence in 12 functional activities. All 12 activities are relevant in ALS. Initial validity was established by documenting that in ALS patients, change in ALSFRS-R scores correlated with change in strength over time, as measured by quantitative neuromuscular strength testing, and with quality of life measures, and predicted survival ([Cedarbaum JM et al 1999](#)). The test-retest reliability is greater than 0.88 for all test items. The advantages of the ALSFRS-R are that the categories are relevant to ALS, it is a sensitive and reliable tool for assessing activities of daily living function in patients with ALS, and has been also validated over the phone ([Kasarski EJ et al 2005](#), [Mannino M et al 2007](#)).

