1.9.3.3. Analysis Population

The primary, secondary and exploratory efficacy endpoints will be analyzed using the ITT population which will be defined as all subjects randomized.

The modified intent to treat (mITT) population will be defined in this study as all participants who were randomized, treated and have at least three ALSFRS-R assessments: one pre-treatment assessments of ALSFRS-R prior to the baseline assessment, a baseline assessment and one post-treatment assessment. Baseline will be the ALSFRS-R assessment at the first transplantation visit (Week 0, Visit 6) prior to treatment. This will permit computing the slope from a linear regression pre- and post-treatment to get a rate of change in ALSFRS-R per month pre-treatment and post-treatment.

No to minimal differences are expected between the mITT and ITT populations, however if there are differences, analysis of the primary endpoint and other select efficacy analyses will also be generated using the mITT population.

The ITT and mITT populations will be analyzed based upon the treatment groups subjects are randomized to.

Supporting efficacy analyses will be conducted using the Efficacy Evaluable (EE) population which will be a subset of the mITT population. The exact criteria used to define the EE population will be finalized prior to locking the database and unblinding the study.

All safety analyses will be conducted on the Safety Population, which will be defined as all participants who were randomized and had at least one transplantation performed.

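### Footnote 12 and Section 1.5.7 conflict with the rest of the protocol on who gets a final visit and what remote contacts collect, and capture of deaths and tracheostomies after withdrawal can end before Week 28

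*Protocol*

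**What the plan says.** **Final visit.** Protocol Table 1, footnote 12 (Section 1.15.1.1): "An ET visit will be conducted only for participants who discontinue the study after treatment, post Visit 6". It adds: "The ET visit will include all the procedures required at study Visit 14", so ALSFRS-R is part of it. SAP Table 2, footnote 12 (Section 4.5), has the same restriction. Protocol Section 1.8.5.2 is wider: "Efforts will be made to follow all participants who discontinue study for any reason". It asks them back for Visit 14, with efficacy as well as safety evaluations.

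**Remote contact.** For those who refuse clinic visits, footnote 12 says "telephone contact by study staff shall be attempted and documented to review for adverse events at each scheduled visit through the remainder of study", and Section 1.5.7 says "telephone contact by study staff shall be attempted and documented to review for AEs at each scheduled visit". The SAP footnote adds home visits but keeps the adverse-event purpose. Section 1.8.5.2 asks for telephone follow-up at the remaining visits without that limit. Section 1.9.1.1, in its paragraph on collecting ALSFRS-R, says "Participants who refuse clinic study visits (or temporarily unable to attend) will be contacted by phone call by the trained site personnel". Section 1.5 has ALSFRS-R given by telephone when it cannot be done in person, and footnote 4 of Table 1 allows this by exception. Section 1.7.1 commits investigators to seek key efficacy data after discontinuation.

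**End of observation.** For those who will not return, Section 1.8.5.2 says of the documented withdrawal date: "The date documented will be considered the last date of contact". It treats that date as the participant's final day in the study. Later events are entered only if the site learns of them within 12 weeks of the last transplant. SAP Section 9.1.1 uses the same 12-week limit for SAEs in participants who discontinue.

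**The concern.** Two sites could follow two parts of the protocol in good faith and collect different data on the same kind of participant. One working from footnote 12 and Section 1.5.7 would offer no final visit to a participant who stops before treatment, and would ask a visit-refuser only about adverse events. One working from Section 1.8.5.2 would do more in both cases.

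At stake are the ALSFRS-R scores that would complete the post-treatment slope, and deaths and tracheostomies after withdrawal. Deaths related to disease progression are non-responders in the primary analysis. CAFS to Week 28, tracheostomy-free survival and survival are key secondary endpoints in SAP Section 3.2.2. Information not sought at the time may not be recoverable at analysis.

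**Working it through.** This is mainly a comparison of passages, with one piece of arithmetic.

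**1. Final visit, by type of participant**

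| Participant | Footnote 12 | Section 1.8.5.2 |
|---|---|---|
| Treated, then discontinues | Visit with all Visit 14 procedures | Visit 14, efficacy and safety |
| Randomised, discontinues before treatment | None | Visit 14, efficacy and safety |

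The conflict is confined to the second row. That row is not hypothetical, because the first reason listed in Section 1.8.5.2 is failure to grow enough cells. Under Section 1.3.1 only marrow from the active arm is processed, so this exit can arise in one arm only.

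**2. Content of remote contacts**

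| Source | Stated content |
|---|---|
| Protocol footnote 12; Section 1.5.7 | Adverse events |
| SAP footnote 12 | Adverse events, by telephone or home visit |
| Section 1.8.5.2 | Remaining visits, content not restricted |
| Sections 1.5, 1.9.1.1; Table 1 footnote 4 | ALSFRS-R by telephone, or calls to visit-refusers in that context |
| Section 1.7.1 | Key efficacy and safety data |

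None of these names vital status or tracheostomy, and Table 1 has no row for either.

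**3. Reach of the 12-week window**

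Transplants are at Weeks 0, 8 and 16. End of window = week of last transplant + 12. Shortfall = 28 − end of window.

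| Doses received | End of window | Shortfall against Week 28 |
|---|---|---|
| 1 | 0 + 12 = Week 12 | 16 weeks |
| 2 | 8 + 12 = Week 20 | 8 weeks |
| 3 | 16 + 12 = Week 28 | 0 weeks |

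These are nominal weeks. A participant with no transplant has no date from which to start the window. Within it, capture depends on the site happening to learn of the event.

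**4. Which analyses are affected**

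The protocol's efficacy population is all randomised: "The primary, secondary and exploratory efficacy endpoints will be analyzed using the ITT population". The SAP tests the primary and key secondary endpoints in mITT, which requires treatment and both slopes (Sections 6.5.2, 8.3.1, 8.4). Never-treated participants therefore matter to the protocol's ITT analysis and to the SAP's supplementary ITT analysis of the primary endpoint. Treated participants who withdraw matter to both populations.

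Under SAP Sections 6.5.2 and 6.8.1, one post-treatment score is enough for a slope. A treated participant who withdraws early and later dies of ALS is a non-responder if the death is known. If it is not known, the early slope decides, and the participant could count as a responder. The same unknown death or tracheostomy is missing from CAFS or the survival analyses. The readable text of SAP Section 8.4 states no censoring date for withdrawn participants.

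**5. The plan's sample size**

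For 35% vs 15%, two-sided 0.05, 90% power, pooled chi-square:

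n = [1.960·√(2·0.25·0.75) + 1.282·√(0.35·0.65 + 0.15·0.85)]² / 0.20² = (1.200 + 0.764)² / 0.04 ≈ 96.4, so 97 per arm.

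This matches the stated figure, and nothing here changes it.

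**The case against.** The strongest reply is that the protocol, read as a whole, already provides for most of these data. Telephone ALSFRS-R appears in Section 1.5 and in the same table as footnote 12. Section 1.5.7 is headed as safety follow-up, so an adverse-event scope is natural there. Treated participants who discontinue and attend do have a final visit with ALSFRS-R. A slope can be computed from few scores. Death is an SAE, so an adverse-event call at each visit can detect it. Section 1.5.8 also provides for alternate contacts when a participant is lost.

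Much of this stands, and it rules out four stronger readings that a reader might infer:

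- *That the protocol limits all telephone follow-up to adverse events.* This is true of footnote 12 and Section 1.5.7 only.
- *That data will be lost.* Conflicting instructions create a risk; they do not establish a loss. For participants who accept calls, deaths should usually surface.
- *That footnote 12 deprives never-treated participants of the primary outcome.* The endpoint is a slope from the first treatment, so one final visit could not supply it. That gap comes from the missing ITT time anchor.
- *That power falls.* Counting an assumed 5% or 10% per arm as non-responders moves power at 100 per arm from 91.0% to 89.0% or 86.7%. The plan gives no drop-out rate and has no rule making missing data non-response. It also says the 35% and 15% already allow for discontinuations, so this may count the loss twice. Nor can such a loss be attributed to this wording.

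The reply does not remove the conflict over the final visit, the two descriptions of the calls, or the end of study set at withdrawal for the very people who are to be telephoned. Adverse-event review is also a weak route to tracheostomy: Section 1.8.1.1 recommends recording procedures as treatment of an event or action taken, not as events of their own.

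**Conclusion.** The point holds as an inconsistency in data-capture instructions, with a real gap in follow-up for survival and tracheostomy. It should be corrected, because the gap reaches key secondary endpoints and the primary death rule even in the SAP's mITT population.

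The only firm figure is the window: it falls 16 weeks short of Week 28 after one dose and 8 weeks short after two. The number of participants, scores or events affected cannot be estimated from the documents. The conclusion assumes that some participants withdraw before the third transplant and that some sites follow the narrower text. It does not assume that any event has been missed.

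**What to change.** Reconcile footnote 12 (protocol and SAP) and Section 1.5.7 with Sections 1.5, 1.7.1, 1.8.5.2 and 1.9.1.1:

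1. Make the final visit in footnote 12 match Section 1.8.5.2, so that it covers all randomised participants who discontinue, including those never treated.
2. State that the remote contacts already planned collect adverse events, ALSFRS-R by telephone, and vital and tracheostomy status at each scheduled visit through Week 28, provided the participant has not withdrawn consent to contact.
3. In Section 1.8.5.2, do not let the withdrawal date close the study for participants who accept calls. In the SAP, censor survival and tracheostomy-free survival at the last date on which status is known.

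The ITT time anchor for never-treated participants, and the conflict between the protocol's ITT and the SAP's mITT, must be settled separately; a final visit alone resolves neither.

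The cost is a short amendment and a little more site time per withdrawn participant. The calls are already planned, and Section 1.9.1.1 puts the ALSFRS-R at 10 minutes.
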